6 STUDY PROCEDURES

6.1 Informed Consent

The Investigator must ensure that written informed consent to participate in the study and written authorization for use and disclosure of protected health information is obtained before including any individual as a subject in the study, and before conducting any study-related assessments. The Investigator must provide the prospective subject with sufficient opportunity to consider whether or not to participate and minimize the possibility of coercion or undue influence.

To participate in the study, a subject must sign and date an IRB-approved consent document. The original, signed documents will be kept with the subjects' files and copies will be provided to the subjects. The informed consent process must be followed, and the subject's participation in the study, must be documented in the subject's medical record/chart.

6.2 Pre-Procedure

Study subjects will have verification of eligibility criteria, a brief general examination including medical history, and pre-procedure assessments as detailed below completed within 30 days prior to undergoing the study procedure. In response to the ongoing coronavirus disease (COVID-19) pandemic, preoperative testing can be completed at the Investigator's discretion. Pre-operative testing should be performed as close to the scheduled study procedure as feasible, but in time to get the results. Up to two urine pregnancy tests must be obtained prior to study procedure for females with child-bearing potential (one at pre-procedure screening and one on the day of the procedure prior to the procedure if pre-procedure screening and procedure are not performed on the same day).

The following pre-treatment assessments will be performed:

- 2D/3D photographic images will be captured. The same standardized photography views will be used throughout the study as documented in the image capture document developed for the study. In addition to the standardized photography views, the baseline 2D/3D photographic images will include an image of the subject performing a grimace to allow for determination of subject eligibility related to the platysmal banding exclusion criteria. **Table 1** illustrates study procedures that will occur at each visit.
- Urine pregnancy test (for females of childbearing potential).
- General physical exam including medical history, vital signs, collection of patient demographic information, and BMI.

Medications subject is taking upon entry into the study should also be documented in the Case Report Forms (CRF). Documentation should include medications that study subjects take on an

elective basis in addition to prescribed medications. Medication used for analgesia and/or anesthesia should be recorded as concomitant medication as well. To ensure the capture of the foregoing information on pre-existing conditions, sites should also be attentive to the need to document without limitation and whenever discovered: (1) all chronic, episodic or ‘as needed’ medications used before study enrollment; (2) prior episodic or ‘as needed’ therapeutic interventions, procedures or hospitalizations; and, (3) recent or planned surgical procedures.

Medications at investigator discretion may be provided as follows:

- Optional Pre-Procedure:
 - Antibiotics: Keflex 500mg BID (first dose just prior, within 60 minutes, to procedure) x 7 days. Alternative, Z-pack.

6.3 Study Procedure

On the day of the procedure and prior to the study procedure, female subjects with child-bearing potential must complete a urine pregnancy test (result must be obtained prior to the procedure).

Medications at investigator discretion may be provided as follows:

- Optional for Procedure (given within 90 minutes prior to procedure):
 - Ativan 2mg or Valium 10-20mg
 - Norco 5-10mg, Hydrocodone 5-10mg, or Ultram 200mg

A responsible driver (friend or family member) is required if these medications are prescribed.

During the study procedure, subjects will be treated with the Renuvion APR device according to the product IFUs and procedures described in this section of the protocol. The bilateral treatment area includes the tissue of the neck (to the posterior border of the sternocleidomastoid muscle) and submental area. Treatment will be performed through three (3) incisions (2 periauricular and 1 submental) with each incision large enough to allow for gas egress, see **Figure 1**. Each incision site will be anesthetized with 1% or 2% Lidocaine with Epinephrine (1:100,000) prior to incision being made.

[figure not shown]

Figure 1: Treatment incisions (2 periauricular and 1 submental).

The treatment area will be infused with standard of care tumescent solution referred to as a Klein solution. The solution consists of 1% or 2% Lidocaine (Plain) to make a 0.2% concentration (double Klein) and Epinephrine 1mg/1ml (1:1,000) and optional Sodium Bicarbonate 8.4% added to Normal Saline or Lactated Ringers. Infuse area with 150-250cc or until the area is taut. To prevent lidocaine toxicity, 35-55mg/kg should not be exceeded¹⁶.

Once infused with Klein solution, undermining of the tissue in the area to be treated will be performed using a cannula 3-4mm in diameter. No energy (i.e. radiofrequency, ultra-sound, or laser energy) or suction will be used during the undermining of the tissue.

After undermining, the Renuvion APR device treatment will be performed using 4-6 treatment passes with settings of 70% power and 1.5 LPM of helium flow with an activation speed of approximately 1-3 cm/s. Prior to performing treatment through each one of the three (3) incisions, the investigator will evaluate activation speed by performing the following steps in the sterile field at a safe distance from the subject:

1. Using a sterile ruler, two parallel lines will be drawn in the sterile field that are 10cm apart.
2. The investigator will place the tip of the device on one of the lines and simulate the activation speed until the tip reaches the second parallel line.
3. While the investigator performs this simulation, an assistant will measure the amount of time it takes for the tip of the device to travel from one line to the other using a stopwatch

or timer. The measured time must be between 3.3 seconds and 10 seconds inclusive to correspond to an activation speed of 1-3 cm/s. The investigator will repeat the simulation until the measured time falls within this range. The final measured simulation time will be recorded in the Procedure CRF for each incision site to provide evaluation of the activation speed at the beginning, middle, and end of the procedure.

6.4 Follow-up Procedures

6.4.1 Immediately Post-Procedure

Following treatment with the Renuvion APR device, surveillance aspiration and manual expression will be performed to evacuate any excess helium gas and/or residual fluid in the treatment area. Surveillance aspiration will be performed using a 10cc locking syringe and a 2.5mm or smaller single hole cannula. Aspiration amount will be limited to 8cc maximum.

Following the procedure, the research staff and the subject will care for the treated areas using the Post-Procedure Care Instructions listed below and the following optional medications at investigator discretion may be provided as follows:

- Optional Post-Procedure
 - Norco 5-10mg, Hydrocodone 5-10mg, or Ultram 200mg
 - Tylenol (OTC) as needed

6.4.2 Post-Procedure Care Instructions

The subject will receive a printed copy of the Take-Home Post-Procedure Care Instructions, see **Appendix C**.

Compression Garment Instructions:

The investigator or directed staff will place a Velcro chin-strap neck compression garment on the subject prior to the subject departing the site. Subjects will be directed to wear the compression garment as follows:

- **Days 0-3:** Wear the neck compression garment for 22 hours per day, removing only for showering/bathing.
- **Days 4-21:** Wear the neck compression garment at night.

Additional Instructions:

Subjects will be instructed to:

- Complete Subject Diary daily through your 14-Day Follow-up Visit.
- Report any treatment effects by noting them in the Subject Diary.
- Call the investigator or study staff if you have a complication outside of the Expected Treatment Effects listed in the Subject Diary.
- Bring your Subject Diary in with you to each visit, through the 14-Day Follow-up Visit when you will turn the Subject Diary into study staff.
- Continue to keep your study doctor and/or study staff aware of any new complications you may experience beyond the 14-Day Follow-up Visit.

6.4.2. Follow-up Visits & Subject Contact outside of Follow-up Visits

Subjects will be asked to return to the study site at the following times post-procedure:

- 1 (+2) day
- 7 (± 1) days
- 14 (± 3) days
- 30 (± 7) days
- 90 (± 10) days
- 180 (± 15) days

Post-procedure assessments and 2D/3D photographic imaging will be performed during the follow-up visits. The same standardized photography views will be used throughout the study as documented in the image capture document developed for the study. **Table 1** illustrates study procedures that will occur at each visit.

Due to the challenges of COVID-19, if a subject is unable to return to the office for an in-person visit, follow-up visits will be conducted virtually. If a visit is completed virtually, missing assessments such as photographs will be documented as a protocol deviation specifically noting COVID-19. Outside of photographs, study investigators and study staff will ensure all other assessments related to each follow-up visit are completed virtually if the visit is done virtually. For virtual visits, the investigator and/or study staff completing the visit and assessments will be identified on the case report form; as well, the manner in which the visit was completed will also be marked on the Case Report Form (i.e. video call, phone call, etc.). Virtual visits should be done via video call if possible, to ensure subject identity. If a telephone call must be done, the investigator and/or study staff must positively identify the subject prior to conducting the virtual visit by requesting the subject to state their address and date of birth. Subjects will be strongly encouraged to come in (albeit safely) for their D180 visit; this visit is vitally important as this is the primary endpoint and photographic images are needed for many of the assessments. Only investigators and study staff who have been trained and delegated to conduct virtual visits as indicated on the delegation log may conduct virtual study visits.

Subjects may be seen for an unscheduled appointment at any time at investigator's discretion. Study staff will contact (phone, text, email, video call at subject's preference) all subjects with ongoing Adverse Events at the following time points, as applicable:

- 21 (± 5) days
- 45 (± 5) days
- 60 (± 5) days
- 75 (± 5) days
- 105 (± 5) days
- 120 (± 5) days
- 135 (± 5) days
- 150 (± 5) days
- 165 (± 5) days

If the subject is unreachable by the preferred method of contact, another method of contact may be attempted. Three attempts will be made to contact the subject before considering the subject contact visit missed and protocol deviation recorded.

Table 1. Study required procedures

	Baseline/ Pre- Procedure Screening ¹	Procedure (Day 0)	1 Day	7 Days	14 Days	30 Days	90 Days	180 Days
			1-3 days	6-8 days	11-17 days	23-37 days	80-100 days	165-195 days
Informed Consent	X							
Assess Inclusion/Exclusion Criteria	X							
Urine Pregnancy Test ²	X	X						
Medical History	X							
General Physical Exam	X							
Review Medications	X	X	X	X	X	X	X	X
2D/3D Photographic Images ³	X ⁶	X ⁸		X	X	X	X	X
Numeric Rating Scale (11-point NRS) ⁴		X ⁷	X	X	X	X	X	X
Study Procedure		X						
Adverse Event Assessment		X	X	X	X	X	X	X
TEN Testing of Sensory Nerves		X	X	X	X	X	As Needed	As Needed
Examination of Facial Motor Nerves		X	X	X	X	X	As Needed	As Needed
Burn Depth Assessment		As Needed	As Needed	As Needed	As Needed	As Needed	As Needed	As Needed
Modified Global Aesthetic Improvement Scale (GAIS) ⁵							X	X
Subject Diary		X			X			
Subject Satisfaction Survey								X

¹ Pre-procedure Screening assessments to take place within 30 days prior to undergoing the procedure.

² Up to two urine pregnancy tests must be obtained prior to study procedure for females with child-bearing potential (one at pre-procedure screening and one on the day of the procedure prior to the procedure if screening and procedure are not performed on the same day).

³Digital photographs will be taken and labeled according to Photography Instructions. 2D images will be extracted from 3D imaging. Both 2D and 3D images will be used for quantitative assessments. Standard positioning and lighting will be used for all photographs.

⁴ To be completed by the study subject on a day of the procedure (prior to the procedure and immediately following the procedure) and at all follow-up visits.

⁵ To be completed by Investigator and study subject at day 90 and day 180 follow-up visits.

⁶ Grimace image taken in addition to standard images at Baseline only.

⁷ NRS pain score will be captured prior to study treatment and immediately (within 60 minutes) after procedure.

⁸ Pre-procedure images may be taken if Baseline/Screening images are not considered acceptable by the quality review team, however if the Baseline/Screening image is acceptable by the quality review team, no additional pre-procedure image needs to be taken.

6.5 Data Collection

Subject demographic information, procedural data, adverse events, device observations, and study required assessments will be documented on the CRFs. Study subjects will complete Numeric Rating Scale and Modified Global Aesthetic Improvement Scale (GAIS) Evaluations at follow-up visits. Subjects will complete a Satisfaction Survey at the 180-day follow-up visit.

6.6 Confidentiality of Data

The Principal Investigator will oversee the conduct of the study and all data will be kept confidential. Confidentiality will be maintained by using subject identification numbers instead of names. Informed consent forms, data collection sheets and records, linking a subject's name with their ID number will be maintained in a locked cabinet or locked office. Information to be stored on the computer will be identified by subject ID and will be password protected.

Data disclosed outside the study team will be de-identified or will only include general group demographic information. Protected Health Information and/or identifiable study data will not be shared with anyone outside the study team or Health System, with the exception of the study sponsor, and federal regulators/ institutional officials for the purposes of auditing.

7 EVALUATION TOOLS

The following evaluation tools will be used in this study:

7.1 2-Dimensional and 3-Dimensional Photography

Two-dimensional (2D) photographic images will be extracted from three-dimensional (3D) images which are captured utilizing the Canfield Scientific, Inc. Vectra M4 Plus 3D imaging system. The same standardized photography views will be used throughout the study as documented in the Image Capture document developed by Canfield for the study. Images will be monitored for quality to ensure standardized images and subject alignment between baseline and follow-up visits. If the Canfield image monitoring team notes differences in head position/tilt or noncompliance with study requirements (headband, tank top, no makeup, no facial expressions, no jewelry), a reshoot will be requested and noted in the Photography Result Report provided by Canfield. Study staff should review photos with particular care during each visit to ensure consistent alignment to prevent having to bring the subject back for a reshoot. If a reshoot is required, the reshoot should be taken within the visit window. Study staff should review Photography Result Reports (provided within 48 hours of image upload) for all images taken to check for reshoot requests.

7.1.1 Independent Photographic Assessments (Primary Effectiveness Endpoint)

Three experienced, blinded photographic reviewers will perform a qualitative analysis/review of the pre-treatment and post-treatment sets of images of each subject in a blinded and randomized order. Each blinded reviewer will choose which image is the post-treatment image. Success will be correct post-treatment image selection by at least 2 out of 3 reviewers. The percentage of subjects with a correct post-treatment image selection will be calculated.

Assessment of each subject's baseline and follow-up images viewed simultaneously will be performed by the Independent Photographic Reviewers (IPR) who will be blinded to the study subject's visit (baseline and follow-up visit). Each IPR will view each subject's randomized pre-treatment and post-treatment images and assess which set of images represent the subject's post-treatment images. Each photograph will have a unique identification number, but the sets of images will not be arranged in any specific order (i.e., randomized order). Canfield will prepare and administer the IPR.

7.1.1.1 Independent Photographic Review Evaluation Process:

1. Each blinded assessor will be provided with identical photos to be assessed. The pre-treatment and post-treatment photos will be consistent in lighting, subject positioning, and focus. Each photo's visit interval, i.e., pre-treatment and post-treatment, will NOT be marked. The images placement (right or left) will be randomly ordered for pre-treatment and post-treatment images. Images for each subject will be grouped together into one set with all pre-treatment and post-treatment images in the same location (right/left) for the subject set.
2. Each blinded assessor will conduct their assessment independently with no input from another blinded assessor.
3. Each blinded assessor compares the Left and Right photo for change that may be striking (substantial and immediately noticeable), readily apparent but modest in nature, or slight and subtle in nature that may require close examination. Assessors should look through

each view and assess change. Enough time should be allowed to do this for each subject, so the assessments are not rushed.

4. The assessor chooses which photo they believe to be the post-treatment photo (i.e., Left photo or Right photo) once all images in the subject set have been reviewed.
5. Post-Analysis Coding of Masked Assessment:
 - If the assessor incorrectly chooses the post-treatment photo, this will be coded as an “Incorrect post-treatment selection”.
 - If the assessor correctly chooses the post-treatment photo, this will be coded as a “Correct post-treatment selection”.
6. Success will be determined by correct identification of post-treatment photographs by at least two out of three blinded, independent reviewers.

7.1.1.2 Independent Photographic Review Training Process:

IPR assessors will participate in a training session prior to completing the IPR. The purpose of the training is to provide guidance to the IPR assessors on the methods for reviewing the study images and to provide sample images from the Phase I safety study for scoring and discussion of the scoring by IPR assessors. Instructions will include that each blinded assessor should pay close attention to changes in:

- Fullness of neck
- Neck lines
- Neck muscle definition
- Jawline definition
- Submental laxity
- Mandibular angle
- Jowling
- Marionette lines
- Overall appearance of the treatment area

IPR assessors will complete a 10-subject mock IPR using images from the Phase I safety study to determine comprehension of the training or need for additional training. The IPR training presentation, 10-subject mock IPR, and mock IPR response instructions/response form are provided as three separate stand-alone documents.

7.1.2 Quantitative Assessment of Lift (Additional Endpoint)

The right profile view of extracted 2D images will be analyzed by Canfield software using marks at the lateral canthus of the eye, anterior nostril margin, and the chin attachment point of the neck to allow for the analysis of submental area as shown in red in the image below, see **Figure 2**. The analysis will compare the population of subjects who respond to treatment by achieving at least 20 mm² of lift of the submental region. Responders will be determined based on change from baseline of area as measured by 2D photography in standard lighting conditions. An area reduction of more than 20 mm² will be considered to be an improvement.

Figure 2: Quantitative Assessment of Submental Area

7.1.3 Quantitative Assessment of Volume (Additional Endpoint)

A series of anatomically defined landmarks on the baseline 3D image will define the submental area of interest for the volume difference measurement, see **Figure 3**. The landmarks will be transposed based on surface tracking to the corresponding follow-up image. The Canfield analysis software will reference the landmarks and create a volume difference model within the area of interest and report measurements of positive, negative, and total volume change.

[figure not shown]

Figure 3: Quantitative Assessment of Submental Volume

7.2 Modified Global Aesthetic Improvement Scale (GAIS) (Additional Endpoint)

The Modified Global Aesthetic Improvement Scale (GAIS) is a subjective rating of improvement in treatment results compared to pre-treatment. The Investigator will grade the overall improvement of treatment area as indicated in **Table 2** by comparing the subject's appearance at follow-up visits against a photograph taken prior to procedure. Likewise, the subject will also rate their improvement compared to pre-treatment as shown in **Table 3**.

The modified GAIS results will be collected at the 90-day and 180-day follow-up visits.

Table 2. Modified Global Aesthetic Improvement Scale Evaluation - Investigator

Table 2: Modified Global Aesthetic Improvement Scale Evaluation - Investigator	
Rating	Description
Very much improved	Optimal cosmetic result from this procedure in this subject
Much improved	Marked improvement in appearance from the initial condition, but not completely optimal for this subject
Improved	Obvious improvement in appearance from the initial condition
No change	The appearance is essentially the same as the original condition
Worse	The appearance is worse than the original condition
Much worse	The appearance is much worse than the original condition
Very much worse	The appearance is very much worse than the original condition

Table 3. Modified Global Aesthetic Improvement Scale Evaluation - Subject

Table 3: Modified Global Aesthetic Improvement Scale Evaluation - Subject	
Rating	
Very much improved	
Much improved	
Improved	
No change	
Worse	
Much worse	
Very much worse	

7.3 Subject Satisfaction Survey (Additional Endpoint)

[figure not shown]
The study subjects will be asked to complete Subject Satisfaction Surveys (see **Appendix A**) at the 180-day follow-up visit.

7.4 Subject Diary

Study subjects will be asked to complete a daily diary (see **Appendix B**) starting from the procedure date (after study procedure, at home) until the 14-day follow-up visit to complete daily 11-point NRS pain assessments and document any complications they have experienced.

7.5 Numeric Rating Scale (NRS) (Primary Safety Endpoint)

The study subjects will be asked to complete a 11-point Numeric Rating Scale (NRS) for the level of pain and discomfort associated with the study procedure – to be completed by the subjects on the day of the procedure prior to the procedure, following the procedure, and at all follow-up visits. The average pain score for the entire region treated will be recorded. Directions to subject will be: *“Please rate the average pain you are experiencing in the treatment area on a scale of 0-10, with 0 being ‘Best/No Pain’ and 10 being the ‘Worst Possible Pain’.”*

Pain will be defined in this study as the average pain reported in the treatment area using the following categories: None (Score of 0), Mild (Score of 1-5), Moderate (Score of 6-7), and Severe (Score of 8-10). Classifications of NRS pain scores have been documented in literature²⁰. Moderate and severe pain/discomfort are considered Adverse Events (AE). Severe subject reported pain does not necessarily correlate to a “severe” adverse event classification. Events will be classified by investigator based on clinical evaluation, the effect to daily activities, and mitigation needed as per **Section 8.6** of this protocol.

Subjects experiencing pain adverse events will be considered resolved when their pain score is documented as returning to a 0 score.

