7.8 Examination of Facial Motor Nerves

Observe:

1. Face at rest for any facial asymmetry not apparent at baseline.
2. Any facial tics, asymmetry of eye blinking or eye closure
3. During smiling

In Palsy:

1. Blink: The eyelid on the affected side closes just a trace later than the opposite eyelid.
2. Nasolabial folds: The weaker one is flatter.
3. Mouth: The affected side droops and participates manifestly less in speaking.

Subjects experiencing motor nerve adverse events will be considered resolved when their motor nerve assessment returns to baseline observations by study investigator.

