8.2 Adverse Event (AE) Definition

An **adverse event** (AE) is any untoward or unfavorable medical occurrence in a human subject, including any abnormal sign (for example, abnormal physical exam or laboratory finding), symptom, or disease temporally associated with the subject's participation in the research, whether or not considered related to the subject's participation in the research.

A preexisting condition (one that is present at the start of the study) will be recorded as an AE only if the frequency, intensity, or the character of the condition worsens during the study period. Neither the condition, hospitalization, prolonged hospitalization, nor surgery are reported as an AE in the following circumstances: hospitalization or prolonged hospitalization for diagnostic or elective surgical procedures for a preexisting condition. Surgery should not be reported as an outcome of an AE if the purpose of the surgery was elective or diagnostic and the outcome was uneventful.

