3 OVERVIEW OF STATISTICAL DESIGN

This is a multi-center, single arm, single-blind (evaluator) prospective study of subjects who are seeking a procedure to reduce the appearance of laxity of the neck and submental regions at up to 8 investigational centers in the United States, with a maximum of 20 study subjects enrolled at each site.

Phase I (n=17) of this study was conducted and provided to the FDA as an interim safety report of safety data including information related to adverse events followed through resolution for all subjects. Phase I of this study was conducted prior to Revision 9 of the study protocol.

Phase II (n=65) of this study will be conducted as the pivotal study to demonstrate the safety and effectiveness of the Renuvion APR Device to improve the appearance of lax tissue in the neck and submental region. Phase II of the study begins with Revision 9 of the study protocol.

Study subjects that meet study eligibility criteria and have provided informed consent will be enrolled in the study. During the procedure, the investigators will use the Renuvion APR handpiece on the neck and submental areas of study subjects with the goal of reducing skin laxity.

Study subjects will be followed immediately following the procedure, and at 1 day, 7 days, 14 days, 30 days, 90 days, and 180 days post-procedure for study assessments. Assessments of

endpoints will use standardized evaluation tools and blinded evaluators as applicable. This includes the use of an independent 3-member evaluation team to eliminate the bias that is likely inherent in the investigators' assessments.

Phase II study enrollment is expected to occur over 6-8 months. Imaging and study assessments will continue through 6 months post-procedure. Total Phase II study duration is expected to be approximately 14 months. The 510(k) application for the device will be submitted based on 180-day post-procedure results. However, this clinical trial will continue until all adverse events are resolved. At that time, the trial will be considered complete, the final results will be determined, and a final report will be prepared.

Table 1 below shows the required evaluations and the schedule on which they are to occur.

Statistical Analysis Plan for the Renuvion APR Study, VP-1902, Rev. No. 3

Table 1: Study Required Procedures

	Baseline/ Pre- Procedure Screening ¹	Procedure (Day 0)	1 Day	7 Days	14 Days	30 Days	90 Days	180 Days

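### Protocol 7.5 closes a pain AE only at a score of 0 and ignores the pre-procedure score, so recorded duration can include pain that was there before treatment

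*Protocol*

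**What the plan says.** Protocol 7.5 classes NRS scores of 6-7 as moderate and 8-10 as severe, and treats both as adverse events. It then fixes the closing rule: "Subjects experiencing pain adverse events will be considered resolved when their pain score is documented as returning to a 0 score". The same section describes the scale as being "for the level of pain and discomfort associated with the study procedure", but the question put to the subject is wider: "Please rate the average pain you are experiencing in the treatment area on a scale of 0-10".

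A baseline value exists. Footnote 7 to Protocol Table 1 states: "NRS pain score will be captured prior to study treatment and immediately (within 60 minutes) after procedure". Nothing in either document links that pre-procedure score to resolution of a pain AE. Protocol 5.2.1 requires healthy subjects and 5.2.2 excludes head and neck injury, but no criterion limits the pre-procedure NRS.

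Protocol 8.1 has the investigator determine resolution dates and asks for accurate AE durations. SAP 3 says that "this clinical trial will continue until all adverse events are resolved".

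**The concern.** The rule works only if every subject starts at 0, and the plan does not require this. A subject whose neck is mildly sore before treatment, whose score rises to 6 or more and then falls back to where it began, has lost the excess caused by the procedure but still has an open AE on paper. The record would show a longer duration, and possibly an event ongoing at day 180, for pain that treatment did not cause.

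The accuracy of the safety listings is at stake, in a single-arm study where pain is the primary safety theme. There is also an operational cost. Under Protocol 8.1 an ongoing AE brings up to nine extra contacts, each a possible protocol deviation if missed. SAP 3 ties completion of the trial to resolution of all AEs.

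**Working it through.** The plan gives no figure on this point, so there is none to reproduce. The check has three parts.

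**1. The rules side by side**

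| Event | Section | Closes at | Type |
|---|---|---|---|
| Pain | Protocol 7.5 | NRS 0 | fixed value |
| Sensory nerve | Protocol 7.7 | TEN score 10/10 | fixed value |
| Motor nerve | Protocol 7.8 | baseline observations | relative to baseline |

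The motor rule reads: "Subjects experiencing motor nerve adverse events will be considered resolved when their motor nerve assessment returns to baseline observations by study investigator". The resolution rules are therefore mixed: two are fixed and one is relative to baseline.

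Let *b* be the pre-procedure score. The written rule closes the AE at the first documented score of 0. A baseline rule would close it at the first score of *b* or lower. If *b* = 0 the two rules are identical. If *b* > 0 and the score never falls below *b*, the written rule is never met. With scores of 2, 7, 2, the subject ends in the mild band (1-5), which would not open an AE, yet the AE stays open.

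**2. Illustration (assumed curves, not document figures)**

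Take score(t) = round[*b* + (peak − *b*) × 0.5^(t/h)], with a peak of 6 or 8, a half-life h of 3 or 7 days, and readings on the protocol's visit and contact days to day 180.

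- *b* = 0, peak 6, h = 3: on day 14, 6 × 0.5^(14/3) = 0.24, which rounds to 0. Both rules close on day 14.
- *b* = 0, peak 6, h = 7: on day 30, 6 × 0.5^(30/7) = 0.31, which rounds to 0. Both rules close on day 30.
- *b* = 2, peak 8, h = 3: on day 14, 2 + 6 × 0.5^(14/3) = 2.24, which rounds to 2. The baseline rule closes on day 14; the written rule is still open on day 180.

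Over *b* = 1, 2 and 3 with both peaks and both half-lives, the baseline rule closes on day 14, 21 or 30. The written rule does not close by day 180 in any of these cases.

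**3. How many subjects**

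Two conditions must hold together: non-zero baseline pain (share p_b) and a pain AE (share p_a). The documents give neither share. Assume p_b from 2% to 10%, p_a from 10% to 45%, and independence. The expected number is 65 × p_b × p_a, and the chance of at least one such subject is 1 − (1 − p_b × p_a)^65.

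- Low: 65 × 0.02 × 0.10 = 0.13; chance of at least one 0.12.
- Middle: 65 × 0.05 × 0.25 = 0.81; chance of at least one 0.56.
- High: 65 × 0.10 × 0.45 = 2.93; chance of at least one 0.95.

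Independence may understate the number, since a subject who starts above 0 has less far to go to reach 6. Within the same range of p_b, the ceiling, with every subject with baseline pain also having a pain AE, is 65 × 0.02 = 1.3 to 65 × 0.10 = 6.5.

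**Effect on planned analyses.** SAP 9.3 classifies subjects by a maximum NRS of 7 or less through the 7-day visit and does not use resolution. The primary effectiveness endpoint is photographic. SAP 9.4 estimates AE rates by time-to-event methods and names no analysis of duration.

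**The case against.** The best defence is that a fixed normal value is a natural endpoint for a numeric scale and that 7.7 uses one too. Requiring 0 can only lengthen pain AEs, so it errs against the device. The population is healthy with head and neck injury excluded, and a single documented 0 closes the event. All of this stands, and it is why the point is small. It does not supply a correct date for the subject whose baseline pain persists, and it leaves a collected baseline unused.

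Four stronger readings are tempting and are not supported.

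- *That 7.5 contradicts 8.2.* Section 8.2 says a pre-existing condition "will be recorded as an AE only if the frequency, intensity, or the character of the condition worsens during the study period". That governs recording, not closing. A rise from 2 to 7 is a worsening, so both sections agree that it is an AE.
- *That such an AE can never resolve.* This holds only if no 0 is ever documented.
- *That the trial could never end.* Protocol 8.4 lets monitoring of any AE stop once it is explained, and 10.6 ends the study when all visits are complete. SAP 3 says otherwise, but that mismatch arises for any unresolved AE. The protocol exits are themselves incomplete here. The stabilisation exit in 8.5 and 10.6 is written for device-related events, while 8.7 directs typical procedural pain to the procedure-related class. An event that is explained also has no resolution date.
- *That 3 to 7 of 65 subjects would be affected.* That is 5-10% of 65 and counts baseline pain alone, without the second condition of a pain AE.

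**Conclusion.** The point holds as a minor defect of definition. For a subject with persistent non-zero baseline pain and a pain AE, the rule in 7.5 gives a resolution date that is too late or missing, which works against the aim in 8.1 of accurate durations. For every subject with a pre-procedure score of 0 it changes nothing. The expected number affected is about 0 to 3 of 65, on assumed rates of 2-10% for baseline pain and 10-45% for pain AEs, taken as independent. The true rates are not in the documents. It would be wrong to infer that AE durations in general are unreliable, or that either primary test is affected.

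**What to change.** State in the SAP, with a matching sentence in Protocol 7.5, that for reporting purposes a pain AE is resolved at the first documented NRS equal to or below the subject's pre-procedure score (0 where that score was 0), and that its duration is computed to that date. Report time to a score of 0 beside it, and tabulate the number of subjects with a non-zero pre-procedure score so that the size of the issue is known.

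The cost is a sentence in each document and one derived variable; no new data are needed. The drawback is that a single pre-procedure reading is noisy. If it happens to be high, the derived date could fall while procedure pain persists at that level. The protocol also does not say whether the reading comes before or after the optional premedication in 6.3. Showing both times covers this.

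Separately, reconcile Protocol 7.5, 8.4, 8.5 and 10.6 with SAP 3 on when follow-up of an unresolved AE ends and when the trial ends. The derivation above concerns reporting only. How long subjects are contacted or followed is for the sponsor and investigators to settle.
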